8.1 Prohibited Medications or Therapies

Medications or therapies that are prohibited during the duration of the study are as follows:

Prior to entry into the study, subjects must not use the medications and/or procedures on the face as specified in Section 5.1.2.

During the study, subjects must not use the following products and/or procedures on the face:

- Topical anti-acne treatments including, but not limited to, OTC acne cleansers or treatments, benzoyl peroxide, antibiotics, azelaic acid, sulfa based products, corticosteroids, and salicylic acid.
- Retinoids including tazarotene, adapalene, and tretinoin.
- Light treatments (including artificial tanning devices), microdermabrasion, or chemical peels.
- Any other investigational drug or use of any investigational device
- Systemic medications with potential anti-acne effects including:
 - Corticosteroids (including intramuscular and intralesional injections). Inhaled, intranasal, or ocular corticosteroids are allowed (see Section 8.2).
 - Antibiotics
 - Spironolactone
 - Retinoid therapy
 - The addition of hormonal contraception
 - Change to pre-existing hormonal contraception
 - Other systemic therapy, which may materially affect the subject's acne in the opinion of the investigator.

Other chronic medications being used at the time of Baseline Visit can be continued at the discretion of the investigator. The reason for any changes in such concomitant therapies should be reported as, or in conjunction with, an AE.

8.2 Allowed Medications or Therapies

Subjects must be on a consistent skin care program (make-up, moisturizers, soap, sunscreen, etc. of their choice, exclusive of RX/OTC acne cleansers) for at least one (1) month prior to enrollment. The subject's skin care regimen will be reviewed and approved prior to their randomization. This skin care program should not contain any OTC products with significant levels of anti-acne ingredients such as retinol or alpha-hydroxy acids (i.e., lactic acid, glycol acid, etc. at greater than 5%).

No additional medications, including OTC preparations, should be used without the knowledge and, if possible, permission of the investigator. Vitamins and mineral supplements are permitted at dosages considered by the investigator as reasonable for maintaining good health. The addition, discontinuation, or dose change of any concomitant medications will be documented in the source documents.

Medications will be permitted, at the discretion of the investigator, to treat local skin reactions, if applicable.

Intranasal, inhaled, and ophthalmic steroids used for the management of allergies, pulmonary disorders, or other conditions exclusive of acne are NOT considered prohibited medications, but should be recorded on the Concomitant Medication Form.

WOCBP taking per protocol allowed hormonal contraception therapy at enrollment must remain on the same treatment for the duration of the trial.

Any changes in concomitant therapies during the study must be recorded on the CRFs. The reason for any changes in concomitant medications or therapies/procedures should be reported and should reflect either a baseline medical condition documented in the medical history of the CRF or an AE.

9. STUDY PROCEDURES

The study will consist of a Screening/Baseline Visit and three (3) scheduled visits.

Specific activities for each study visit are listed below.

9.1 Visit 1 (Day 1): Screening/Baseline

Subjects can be screened for the study up to 45 days before Visit 1. During screening, the study requirements will be reviewed, written informed consent/assent obtained, and eligibility confirmed. If applicable, the washout from prohibited medications or treatments will be determined and implemented. Subjects who require "washout" for longer than 45 days will be re-consented.

At Screening, the investigator or designee will:

- Obtain a signed, written informed consent (unless the subject signed a consent within the past 45 days). Note: a subject under 18 years of age must provide written informed assent and be accompanied by the parent or legal guardian at the time of assent/consent signing. The parent or legal guardian must provide informed consent for the subject. If a subject becomes 18 years of age during the study, the subject must provide written informed consent at that time to continue study participation.
- Complete review and documentation of the subject's medical and dermatological history and demographic information.
- Record any concomitant medications and therapies.
- Confirm the subject meets the inclusion/exclusion criteria.
- Have subject complete washout from any prohibited medications, if necessary.

Once the Screening procedures have been completed, the investigator or designee will:

- Perform a dermatologic exam and brief physical exam (including vital signs, height, and weight).
- Perform a Fitzpatrick Skin Type assessment (see Section 10.3).
- Perform a UPT for all WOCBP (see Section 5.1.1 for definition). The results must be negative for the subject to be enrolled into the study.
- Perform an ECG.
- Perform IGA (see Section 10.1) and acne lesion counts (see Section 10.2) prior to the first application of the test article.
- Record Baseline LSRs (prior to application of the test article) (see Section 10.4).
- Perform photography for all subjects at all sites (see Section 11).
- If the subject meets the inclusion/exclusion criteria, randomize the subject to the next available (lowest) subject number.
- Weigh and dispense initial tube(s) of test article.
- Complete the Study Medication Accountability Log.
- Dispense the Subject Instruction Sheet to the subject and parent/guardian (if applicable) (Appendix 1).
- Dispense the Subject Diary (Appendix 2) to the subject and parent/guardian (if applicable) and provide completion instructions.
- Instruct the subject and parent/guardian (if applicable) where and how to apply the initial dose of test article to the acne lesions on the face following the procedures in Section 6.2. The first application should occur in the office under supervision of the study staff.
- Record any AEs and LSRs (see Section 10.4) after the initial application of the test article.
- Instruct the subject and parent/guardian (if applicable) to apply the test article (about 1 gram) to the whole face twice per day, with at least eight (8) hours between applications.
- Update the Screening and Enrollment Log.
- Schedule Visit 2 (Week 4).

9.2 Visits 2 (Week 4) and 3 (Week 8)

The visit windows for Visits 2 and 3 are Day 29 \pm 5 and Day 57 \pm 7, respectively.

At these visits, the investigator or designee will:

- Observe/query the subject about any changes in his/her health since the previous study visit, including concomitant medications/therapies, and document the findings.
- Assess any LSRs associated with the subject's acne or the topical application of the test article (see Section 10.4).

- Initiate/update the appropriate AE form, if applicable.
- Perform a UPT for all WOCBP (see Section 5.1.1 for definition).
- Perform photography (see Section 11).
- Perform IGA (see Section 10.1) and acne lesion counts (see Section 10.2).
- Collect and dispense another (new) Subject Diary, if necessary (Appendix 2).
- Collect and weigh used tubes of test article and weigh/dispense additional tubes, if necessary (see Appendix 3). If subject is under or over utilizing the test article remember to re-educate them regarding proper use and application.
- Complete the Study Medication Accountability Log.
- Review subject instructions on the proper application of the test article (Appendix 1) with the subject and parent/guardian (if applicable) and the recommended amount of test article per application, as well as review and discuss any discrepancies or concerns with the subject regarding their use of the diary in addition to the amount of test article used since the last visit, if applicable. Subjects who have missed multiple applications of the test article may be discontinued from the study, at the discretion of the investigator.
- Instruct the subject and parent/guardian (if applicable) to continue application of the test article (about 1 gram) to the whole face twice per day, with at least eight (8) hours between applications.
- Schedule the next visit.

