6.2 Instructions for Use and Application

At the first visit, the subjects will be instructed to wash their entire face (the area to be treated) with mild soap and water and then dry the area gently. The study staff will then instruct the subject and parent/guardian (if applicable) on how to dispense the cream, how much of the test article to use, and where to apply the assigned test article. The first application of cream should be applied in the office at Visit 1 under supervision of the study staff after subject has been deemed eligible. Typically, about 1 gram of the cream will be dispensed onto a fingertip and applied to the face by dabbing small amounts gently on multiple regions of the face (e.g., forehead, nose, cheeks, chin). Using a fingertip, the cream will be spread to provide a thin, uniform layer of the cream **over the entire face**.

Subjects and parents/guardians (if applicable) will be instructed to apply the cream to the whole face twice daily (morning and in the evening) for 12 weeks. The subject should ideally allow at least eight (8) hours between applications. All subjects should not wash the treated area for at least four (4) hours following test article application; and **MUST NOT APPLY THE TEST ARTICLE WITHIN FOUR (4) HOURS PRIOR TO ANY STUDY VISIT**.

Subjects will be provided with a Subject Diary to record the dates and time of application. Subjects will be instructed to only apply the study cream to the face as instructed by the investigator or designated study personnel. **Note: The dispensing, recording, and application of the test article by the subject may require adult supervision by the subject's parent/guardian.**

Subject and parent/guardian (if applicable) will also be provided with a Subject Instruction Sheet providing them with instructions on how to use and store the cream at home during the study period.

Subject and parent/guardian (if applicable) will be instructed to bring all the containers of cream (used and unused) and their completed diaries to each visit. The study staff will weigh all the returned containers and will record the weights on the appropriate study medication accountability logs and case report forms (CRFs).

Subjects who are not compliant with applying the creams as instructed (determined from subject diaries and/or the weight of test article used) may be discontinued from the study.

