13.1 Completion of the Study

Each subject who completes the 12-week course of treatment as specified in this protocol will have completed the study.

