13.2 Subject Discontinuation

A subject may be withdrawn from the study prior to completion for any of the following reasons:

- Whenever the subject or the subject's parent/guardian decides it is in the subject's best interest to be withdrawn, Note: if the subject or parent/guardian decides to withdraw from the study due to an AE then it should be classified as withdrawal due to an AE.
- Whenever the investigator decides it is in the subject's best interest to be withdrawn
- AEs
- Worsening of condition or treatment failure (in the opinion of the investigator)
- Noncompliance
- Pregnancy
- Lost to follow-up
- Sponsor administrative reasons

If a subject withdraws prematurely during the 12-week treatment period for any reason, the Visit 4 procedures should be completed at that time. Subjects who withdraw prematurely will not be replaced. When a subject is withdrawn from the study for a treatment-related AE (i.e., possibly, probably or definitely related as defined in Section

14), when possible, the subject should be followed until resolution or stabilization of the AE.

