17.3 Statistical Methods

All statistical processing will be performed using SAS[®] unless otherwise stated. Summary tables (descriptive statistics and/or frequency tables) will be provided for baseline variables, efficacy variables, and safety variables. Continuous variables will be described by descriptive statistics (n, mean, standard deviation, CV%, minimum, median, and maximum). Frequency counts and percentage of subjects within each category are provided for categorical data. Summaries will be provided for each treatment group.

The Safety set will include all subjects who received at least one application of the test article. The ITT set will include all randomized subjects. The PP set will be a subset of the ITT set and will include subjects who completed the study without any significant protocol deviations. The analysis of safety will be conducted on the Safety set. The analysis of efficacy will be conducted on both the ITT and PP sets, with the ITT set considered as the primary set for statistical analysis. Multiple imputation will be used to impute missing values for the primary endpoints and absolute change in total lesions count (S1) in the ITT analyses. Sensitivity analyses will be performed to investigate the robustness of the results obtained on the ITT set for the primary endpoints (change from Baseline in non-inflammatory and inflammatory lesion counts and IGA “success” at Week 12). Missing values for the other secondary endpoints (i.e., S2-S4: percent change in lesions counts) will be calculated using the values obtained from the multiple imputation of the primary efficacy endpoints and secondary efficacy endpoint #1 (S1).

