### 6.3 Evaluation of Treatment Compliance

Compliance to the test article will be evaluated at each visit and overall according to the following formula:

$$\text{Compliance} = 100 \times \frac{\text{Number of actual applications}}{\text{Number of scheduled applications}}$$

Non-compliance will be defined as a compliance value less than 80% and subjects with an overall compliance not evaluable due to missing data or less than 80% will be excluded from the Per Protocol Set (see paragraph 6.2.1).

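### Noncompliant subjects may be taken out of the study, so obtainable Week 12 outcomes are lost to the ITT analysis

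*Protocol*

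**What the plan says.** Three parts of the protocol let noncompliance end study participation, and not only use of the cream.

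- Section 9.2, for the Week 4 and Week 8 visits: "Subjects who have missed multiple applications of the test article may be discontinued from the study, at the discretion of the investigator".
- Section 6.2 applies the same sanction to "Subjects who are not compliant with applying the creams as instructed", judged from the diary, the weight of cream used, or both.
- Section 13.2 opens its list with "A subject may be withdrawn from the study prior to completion for any of the following reasons", and noncompliance is on that list.

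On what happens next, Section 13.2 states: "If a subject withdraws prematurely during the 12-week treatment period for any reason, the Visit 4 procedures should be completed at that time". It adds: "Subjects who withdraw prematurely will not be replaced". No later visit is described. Section 13.1 ties finishing the study to finishing treatment: "Each subject who completes the 12-week course of treatment as specified in this protocol will have completed the study".

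On the analysis side, Protocol 17.3 states: "The ITT set will include all randomized subjects". All three primary endpoints are measured at Week 12 (Protocol 17.1.1, SAP 4.1.1). SAP 6.4.1 and 6.4.2 fill missing primary outcomes by multiple imputation under MAR, in a single process that does not use treatment arm. Four single-value replacements (missing as worst value, worst case, LOCF, BOCF) and a PP analysis serve as sensitivity analyses. For the PP set, SAP 6.3 states that "subjects with an overall compliance not evaluable due to missing data or less than 80% will be excluded from the Per Protocol Set".

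**The concern.** The primary analysis needs a Week 12 outcome from everyone randomised, yet the protocol permits that outcome to go uncollected in subjects who may be perfectly able to attend. Removal brings no analytical benefit, because the PP set already leaves out poor compliers.

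The trigger is also looser than the PP rule. More than one missed application has no upper or lower limit, and the decision is left to each investigator across 48 enrolling sites. A subject who would have met the 80% rule could be removed, and would then leave the PP set as well, because SAP 6.2.1 requires Week 12 primary assessments.

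At stake are avoidable missing data in the primary analysis, more dependence on an imputation model, and some power on inflammatory lesion count (P3), the endpoint that sets the sample size.

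**Working it through.** **Inputs from the documents**
- Two-sided alpha 0.05 and beta 0.033 per primary test (Protocol 17.2, SAP 4.3), so z = 1.960 and 1.838.
- P3: -15 versus -10, a difference of 5, SD 17 (protocol synopsis, SAP 4.3.3). Protocol 17.2 prints -14 versus -11 beside the same 334. A difference of 3 would need 927 per group, so 334 belongs to the difference of 5 used here.
- Phase 2 least-squares means -14.47 and -10.62, a difference of 3.85 (SAP 4.3.3).
- At least 350 per group.

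**Assumptions (the documents give no figure)**
- 10% of each arm is removed for noncompliance, with 5% and 20% as a range.
- Noncompliers gain a share g of the effect, between 0 and 0.5.
- Values imputed without regard to arm carry no difference between arms.

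**Step 1: the plan's figure.** N = 2 × 17² × (1.960 + 1.838)² / 5² = 333.5, rounded up to 334 per group. This matches.

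**Step 2: the removal trigger against the PP rule.** Twelve weeks twice daily is 2 × 84 = 168 applications. Missing 33 leaves 135/168 = 80.4%, still compliant for PP. Two missed applications could already satisfy the wording of Section 9.2.

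**Step 3: the difference under each policy.** With planned difference D and 10% noncompliers:
- followed to Week 12: d = D × (1 − 0.10 × (1 − g));
- removed and imputed without arm: d = D × (1 − 0.10).

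**Step 4: power.** Power = Φ(d/SE − 1.96), with SE = 17 × √(2/350) = 1.285.

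| Case | d if D = 5 | Power | d if D = 3.85 | Power |
|---|---|---|---|---|
| No noncompliance | 5.00 | 97.3% | 3.85 | 85.0% |
| Followed, g = 0.5 | 4.75 | 95.9% | 3.66 | 81.2% |
| Followed, g = 0 | 4.50 | 93.8% | 3.47 | 76.9% |
| Removed, imputed without arm | 4.50 | 93.8% | 3.47 | 76.9% |

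The cost of not following these subjects is the gap between the last row and the two rows above it: 0 to about 2 points at D = 5, and 0 to about 4 points at D = 3.85.

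**Step 5: range.** At D = 5 and 5% removed, following gives d = 4.75 to 4.875 (95.9% to 96.7%) and removal gives 4.75 (95.9%), a loss of 0 to about 1 point. At 20%, following gives 4.0 to 4.5 (87.6% to 93.8%) and removal gives 4.0 (87.6%), a loss of 0 to about 6 points.

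**Step 6: lost information.** At 10% removed, 350 × 0.9 = 315 per arm are observed. With d = 4.5 and 315 per arm, power is 91.3%, up to 93.8 − 91.3 = 2.5 points lower again. This is rough, because it treats imputed subjects as adding no information.

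**The case against.** The case for leaving the text alone has real substance.

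- **An assessment is taken on leaving.** Section 13.2 and the first footnote of the schedule of events require the Visit 4 procedures, including IGA and lesion counts. This stands, so it would be wrong to say that efficacy data are simply deleted. But a visit at Week 4 or 8 is not a Week 12 outcome, and the SAP does not say whether it may serve as one.
- **Removal is optional and may be rare.** The rule is permissive, Section 9.2 also tells staff to re-educate under- and over-users, and eligibility screens out unreliable subjects. This stands, and the frequency is unknown.
- **Sensitivity analyses are planned.** Worst value, worst case, LOCF, BOCF and PP all test the result. They probe the assumption, but none recovers the missing value.
- **Most of the power drop is not caused by removal.** A reader might compare 97.3% with 93.8%, or 85% with 77%. That would charge removal with dilution that noncompliance causes even under full follow-up. The right comparator is the true ITT difference of 4.5 to 4.75.

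A reader might also infer that the effect would be overstated, because noncompliers are imputed as if they had complied. Imputation from compliers in the same arm would return about 5 against a true 4.5 to 4.75, or 5% to 11% too high (5/4.75 = 1.05, 5/4.5 = 1.11). SAP 6.4.1 rules that method out, since its single imputation process does not use arm. Noncompliers who are not removed also contribute to the model. A difference in removal between arms is likewise unsupported in a double-blind trial.

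**Conclusion.** The point holds as one about avoidable missing data. Followed as written, the plan can lose Week 12 primary outcomes that were obtainable, for no analytical gain. It then relies on MAR imputation that ignores arm, or on an off-time value under a rule the SAP does not state.

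The likely size is modest. At an assumed 10% removal, dilution costs about 0 to 2 points of P3 power, or 0 to 4 points at the Phase 2 difference, plus some lost information. If noncompliers truly gain nothing, dilution costs nothing.

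These figures rest on the assumed removal rate, on g between 0 and 0.5, and on imputed values carrying no effect. The SAP does not list the variables in its imputation model. If earlier post-baseline counts are included, part of the effect would carry through and the dilution would be smaller. The change is worth making because it is cheap and protects the primary analysis, not because the trial fails without it.

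**What to change.** In Protocol 6.2, 9.2 and 13.2, state that noncompliance alone does not end study follow-up. These subjects keep their scheduled visits through Week 12 unless consent is withdrawn, and their observed Week 12 values are used in the ITT analysis. PP handling stays as it is, and no decision about the test article is affected.

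The SAP should also say whether assessments made at early termination count as Week 12 values or are treated as missing at Week 12.

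The cost is a protocol clarification, one SAP sentence, and visits already planned for what is probably a small number of subjects. The SAP reports 732 subjects as already enrolled. If their follow-up has ended, the collection change can help only later trials, and the SAP rule is the part still open here.

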9.3 Visit 4 (Week 12): End of Study

The visit window for Visit 4 is Day 85 \pm 10.

At this visit, the investigator or designee will:

- Observe/query the subject about any changes in his/her health since the previous study visit, including concomitant medications/therapies, and document the findings.
- Assess any LSRs associated with the subject's acne or the topical application of the test article (see Section 10.4).
- Initiate/update the appropriate AE form, if applicable.
- Perform a UPT for all WOCBP (see Section 5.1.1 for definition).
- Perform an ECG.
- Perform photography (see Section 11).
- Perform IGA (see Section 10.1) and acne lesion counts (see Section 10.2).
- Collect the Subject Diary (Appendix 2).
- Collect and weigh used and unused tubes of test articles (see Appendix 3).
- Complete the Study Medication Accountability Log.
- Complete End of Study Form and discharge subject from the study.

10. CLINICAL EVALUATIONS

The following clinical evaluations will be performed according to the schedules indicated during the study. The same investigator should complete the evaluations for a given subject throughout the study. If this becomes impossible a sub-investigator with overlapping experience with the subject and the study should complete the evaluations.

